3.2 Exclusion Criteria

- 3.2.1 Pregnancy or Breast-Feeding: Patients who are pregnant or breast-feeding are not eligible for this study due to the potential for fetal or teratogenic toxicities. Negative pregnancy tests must be obtained in female patients who are post-menarchal.
- 3.2.2 Major surgery within 14 days prior to start of treatment. No time limitations after minor surgery (eg: core biopsy or central line placement)

- 3.2.3 Current evidence of GIST, alveolar soft part sarcoma, or dermatofibrosarcoma
- 3.2.4 Concomitant Medications:
 - a. Growth factor(s): Growth factors that support platelet or white cell number or function must not have been administered within the 7 days prior to enrollment (14 days if pegfilgrastim).
 - b. Corticosteroids: Patients receiving corticosteroids who have not been on a stable or decreasing dose of corticosteroid for the 7 days prior to enrollment are not eligible.
 - c. Investigational Drugs: Patients who are currently receiving another investigational drug are not eligible.
 - d. Anti-cancer Agents: Patients who are currently receiving other anti-cancer agents are not eligible.
 - e. Enzyme-inducing anticonvulsants or other medications: Patients who are currently receiving the enzyme inducing anticonvulsants: phenytoin, phenobarbital, carbamazepine, oxcarbazepine are not eligible. Patients who are currently taking rifampin, voriconazole, itraconazole, ketoconazole, aprepitant, or St. John's Wort are not eligible. See Appendix B for more details
 - f. Anticoagulants: Use of warfarin is not allowed while on study. Patients already on warfarin should use alternative anticoagulants while on this study. Warfarin must not have been administered within 7 days of starting protocol therapy.
 - g. Medications that prolong the QTc: Patients receiving medications listed in Appendix C are not eligible.
- 3.2.5 Infection: Patients who have an uncontrolled infection, or who are currently receiving treatment for *C difficile* infection.
- 3.2.6 Patients with a history of allergic reactions attributed to eribulin or irinotecan.
- 3.2.7 Patients with documented allergy to cephalosporins.
- 3.2.8 Patients with CNS tumors or known brain metastases.
- 3.2.9 Patients with known metastatic tumor in the bone marrow.
- 3.2.10 Patients who in the opinion of the investigator may not be able to comply with the safety monitoring requirements of the study.
- 3.2.11 Uncontrolled intercurrent illness that would limit compliance with study requirements.
- 3.2.12 HIV-positive patients on combination antiretroviral therapy are ineligible because of the potential for pharmacokinetic interactions with eribulin and irinotecan. In addition, these patients are at increased risk of lethal infections when treated with marrow-suppressive therapy.

3.3 Inclusion of Women and Minorities

Both males and females of all races and ethnic groups are eligible for this trial.

4. REGISTRATION PROCEDURES

4.1 Enrollment Guidelines

Eligible patients will be identified by the principal investigator and co-investigators of this study. Potentially eligible patients will be pre-screened by the investigators, study personnel, or the Principal Investigator by conducting a brief medical chart review to determine key eligibility criteria.

Registration of all participants must occur before any study-related procedures. Staff will be available to register participants Monday thru Friday, from 8:00 AM to 5:00 PM Mountain Standard Time. In emergency situations, where a patient must be registered during holidays or off-hours, you may call the research coordinator at [contact]. You may not register a participant if a slot has not been reserved.

Please follow these steps to register a participant:

- 1. Obtain written informed consent/assent prior to any study related procedures.
- 2. Complete the eligibility checklist. The local investigator must sign the checklist confirming that eligibility has been reviewed.
- 3. Send the signed eligibility checklist along with supporting source documents, including the consent/assent, to the research coordinator at Children's Hospital Colorado (CHCO). You may send all the documents via fax or email. Please fax to [contact] or email the CHCO coordinator listed in the front of the protocol.
- 4. An investigator at CHCO will review and confirm eligibility. The eligibility will be signed by the investigator and returned to the site. An email or registration confirmation will be sent to the overall study PI, local investigator and local study coordinator. Patients will receive eribulin at the assigned dose level throughout their treatment unless dose modifications occur as outlined in Section 6.0.
- 5. The participant will be assigned a participant number that includes the site number followed by the sequential order of participants enrolled local; site #_sequential number (e.g., 01_01, then 01_02 for site number 01)

4.2 Compliance with Laws and Regulations

The study will be conducted in accordance with U.S. Food and Drug Administration (FDA) and International Conference on Harmonization (ICH) Guidelines for Good Clinical Practice (GCP), the Declaration of Helsinki, any applicable local health authority, and Institutional Review Board (IRB) requirements. The PI or designee will be responsible for obtaining continuing and not less than annual IRB re-approval throughout the duration of the study. Copies of the Investigator's annual report to the IRB and copies of the IRB continuance of approval must maintained by the the appropriate participating site and the University of Colorado. The PI or designee is also responsible for notifying the Data and Safety Monitoring Committee (DSMC) and the participating sites IRB of record of any significant adverse events that are serious and/or unexpected, as per standard operating procedure for those entities. In addition, the DSMC will review all adverse events at routine intervals as per standard operating procedures

5. TREATMENT PLAN

5.1 Enrollment and Screening Process

Any testing done specifically for research purposes related to this study should be performed only after written informed consent is obtained.

5.2 Agent Administration

Treatment may be administered either in the inpatient or outpatient setting. Reported adverse events and potential risks are described in Section 7. Appropriate dose modifications are described in Section 6. No investigational or commercial agents or therapies other than those described below may be administered with the intent to treat the patient's malignancy.

Dose Escalation Schedule				
		Dose		
Dose Level	Irinotecan (mg/m ² /day)	Eribulin (mg/m²/dose)		
Level 0	90	0.8		
STARTING DOSE: Level 1	90	1.1		
Level 2	90	1.4		

There will be no intra-patient dose escalations.

Therapy Delivery Map – Cycle #		
	Patient name	DOB

DRUG	ROUTE	DOSAGE	DAYS	Observa	ations
Eribulin	IV over 2-5 min	See dose escalation scheme	1,8	a. 1 b. 1	History Physical Exam
Irinotecan	РО	90 mg/m ² /dose	1-5 (On day 1, irinotecan is given at least 15 minutes after eribulin)	c. (d. (e.)	(Ht/Wt/VS/ performance status) CMP CBC Pharmacokinetics ¹
Cefixime	PO	400 mg/day	-1 through 8		

Ht _____ Wt ____ BSA _____ Dose level = _____

Assigned Eribulin dose is $_{mg/m^2} = _{mg}$

Date	Date	Day	Eribulin	Irinotecan	Cefixime	Studies
Due	Given					
		-1 (20*)			mg	
		0 (21*)			mg	
		1	mg	mg	mg	a, b, c, d, e ¹
		2		mg	mg	
		3		mg	mg	
		4		mg	mg	$e (optional)^2$
		5		mg	mg	
		6			mg	
		7			mg	
		8	mg		mg	b, c^3 , d^4 , e^1
		15				c^{3}, d^{4}
		20			mg	
		21			mg	

¹Blood samples for pharmacokinetic testing will be obtained pre-dose, 0.25, 1, 1.5, 2, 4, and 5 hours after the administration of eribulin on day 1 and prior to day 8 dose with regularly obtained labs (see Appendix g for Pharmacokinetic Study Form). **These samples will only be collected in the first treatment cycle.**

² An optional single pharmacokinetic sample may be collected anytime between 24-96 hours if labs are being obtained at UK for other purposes.

³CMP must be drawn weekly during cycle 1, and then may be drawn only at the start of subsequent cycles ⁴CBC with differential should be drawn **twice weekly during the first cycle**, and then must be drawn at least weekly during subsequent cycles

On day 1 in which eribulin and oral irinotecan are administered concurrently, the eribulin should precede irinotecan by at least 15 minutes.

Subsequent cycles should start after day 21 as soon as the ANC \geq 1,000/µL and platelets \geq 100,000/µL, and eligibility criteria are met for renal and hepatic function (Section 3.1). This start date could vary by 3 days.

5.2.1 Administration of Eribulin

Aseptically withdraw the required amount of eribulin mesylate from the single-use vial and administer undiluted or diluted in 0.9% Sodium Chloride Injection, USP intravenously over 2 to 5 minutes.

5.2.2 Administration of Oral Irinotecan

For oral use, the appropriate volume of irinotecan solution (20 mg/ml) is drawn up undiluted into a plastic oral syringe. Each dose is to be mixed with juice (crangrape, cranapple, cranberry, or other "cran" juice) immediately before administration. The oral syringes containing undiluted irinotecan are stable for 21 days when stored in a refrigerator. Irinotecan has a very unpleasant flavor, and so the juice will be used to mask the drug taste (Appendix D). See protocol for premedication and supportive care measures.

If emesis occurs within 20 minutes of taking a dose of irinotecan, then the dose may be repeated once. If emesis occurs after 20 minutes, the dose should not be repeated. Instructions for administration of oral irinotecan are included in Appendix D and a copy of Appendix B, outlining potential drug interactions with irinotecan, should be given to the patient.

5.3 Supportive Care

5.3.1 Antiemetics

Premedication with a 5-HT₃ antagonist is recommended 30 minutes prior to daily irinotecan doses. Aprepitant and/or steroids should not be used as antiemetics on this study due to effects on CYP3A4 and potential interference with irinotecan metabolism.

5.3.2 Growth Factors

Patients should not receive growth factors, including GMCSF, GCSF, or pegylated GCSF unless indicated in the Dose Modification section, 6.1.

5.3.3 Concomitant Medications

Eribulin has been associated with prolonged QTc, so medications that prolong QTc should be avoided when possible. A list of medications that prolong QTc is provided in Appendix C.

5.3.4 Supportive Care

Appropriate antibiotics, blood products, antiemetics, fluids, and general supportive case are to be used as necessary.

5.3.5 Prophylaxis for Irinotecan-Associated Diarrhea

Cefixime or an available equivalent antibiotic will be used to reduce irinotecan-associated diarrhea as previously mentioned [44, 45]. Antibiotic treatment should start at least two days prior to the start of irinotecan. This antibiotic therapy should continue until 3 days after the last dose of irinotecan.

5.3.6 Concomitant Medications for Diarrhea and Abdominal Cramping

Patients and their families will be instructed to contact their physician if diarrhea occurs. Any patient who develops diarrhea or abdominal cramping within the first 4 hours after oral administration of irinotecan should receive atropine intravenously at a dose of 0.01 mg/kg (maximum 0.4 mg). This so-called "early onset diarrhea" is often presaged by cholinergic manifestations such as diaphoresis and abdominal cramping. Because patients are treated with irinotecan over multiple days, it may be difficult to distinguish immediate from delayed diarrhea. Patients with presumed immediate diarrhea who do not improve with atropine, or patients who develop diarrhea more than 4 hours after receiving irinotecan, should be given treatment with oral loperamide for late onset diarrhea as outlined below.

All patients will receive a copy of instructions for the use of loperamide if/when diarrhea occurs (Appendix D). Each family will be provided with this antidiarrheal medicine with instructions to start at the first episode of poorly formed or loose stools, or at the earliest onset of bowel movements more frequent than normally expected for the patient.

Loperamide (1 mg/5 ml or 1 caplet = 2 mg) dosing guidelines for diarrhea: Weight \geq 43 kg (\geq 95 pounds): Take 4 teaspoonfuls or 2 caplets after the first loose stool, followed by two teaspoonfuls or one caplet every two hours as needed. Weight 20 kg to 43 kg (\leq 94 pounds): Take 2 teaspoonfuls or 1 caplet after the first loose stool, followed by one teaspoonful or one-half caplet every 2 hours as needed.

Because patients will be receiving prolonged exposure to antibiotics (i.e., cefixime), patients having significant diarrhea should have stool samples evaluated for *C difficile* toxin, as this is a potentially treatable cause of diarrhea. If patients have fever with diarrhea, or bloody diarrhea, evaluation of stools for bacterial culture should also be performed.

If there is failure of loperamide to control diarrhea after 24 hours of use, patients may receive octreotide (SandostatinTM) at the dose of 10 micrograms/kg/dose subcutaneously every 12 hours x 3 days.

5.4 Criteria for Starting Subsequent Cycles of Therapy

A cycle may be repeated if:

• The patient has no evidence of disease progression as assessed clinically and/or with imaging studies

- The patient meets eligibility criteria for hematopoietic, renal, and liver function (Section 3.1)
- The patient has not met any criteria for removal from protocol therapy as described in Section 5.9

Patients who experience dose-limiting toxicity but do not have evidence of progressive disease may be eligible for additional protocol therapy as described in Section 6.0.

5.5 Definition of Dose-Limiting Toxicity

Dose-limiting toxicity (DLT) will be defined as any of the following events, detailed in Sections 5.5.2 and 5.5.3 that are possibly, probably or definitely attributable to protocol therapy. Decisions regarding the estimation of the recommended phase II dose and assigning treatment dosages to subsequent patients will be made on observations occurring in the first cycle of therapy.

5.5.1 Grading of Adverse Events

Adverse events (toxicities) will be graded according to the NCI Common Terminology Criteria for Adverse Events v4.02 (CTCAE) http://ctep.cancer.gov/reporting/ctc.html.

Any suspected or confirmed dose-limiting toxicity should be reported within 24 hours to the coordinating center and Principal Investigators at both centers.

5.5.2 Non-Hematological Dose-Limiting Toxicity

Non-hematological dose-limiting toxicity is defined as any Grade 3 or Grade 4 nonhematological toxicity that is possibly, probably or definitely attributable to the investigational drugs with the specific exclusion of:

- Grade 3 nausea, vomiting or dehydration
- Grade 3 diarrhea \leq 3 days
- Grade 3 diarrhea regardless of duration if patient did not receive appropriate supportive care (cefixime, loperamide, or atropine as outlined in Section 5.3)
- Grade 3 transaminase (AST/ALT) elevation that returns to grade ≤ 1 or baseline prior to the time for the next treatment cycle
- Grade 3 GGT
- Grade 3 fatigue \leq 3 days
- Grade 3 fever, febrile neutropenia, or infection
- Grade 3 electrolyte abnormalities (Na, K, Cl, CO2, Ca, Mg, Phosphate) that improve to \leq grade 2 within 7 days, with or without supplements

Allergic reactions that necessitate discontinuation of the study drugs will not be considered a dose-limiting toxicity.

Patients who develop \geq Grade 3 QTc prolongation (\geq 501 msec) at any time must be removed from protocol therapy.

5.5.3 Hematological Dose-Limiting Toxicity

Hematologic DLT will be defined as any of the following:

- Greater than 7 days duration of either grade 4 neutropenia or grade 4 thrombocytopenia of > 7 days duration
- Grade 3 or 4 thrombocytopenia that requires platelet transfusions on greater than 2 occasions during a cycle.
- Failure to recover blood counts to eligibility criteria that cause a delay of \geq 14 days between treatment cycles.

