2.4 Rationale for Combining Eribulin and Irinotecan

While the planned testing of eribulin as a single agent in the pediatric population is necessary, nearly all pediatric cancers are treated with drug combinations, and searching for a suitable therapeutic partner for eribulin is the next logical step in development of this drug. We propose testing the combination of eribulin and oral irinotecan in a phase I trial designed to determine the recommended phase II dose of eribulin when combined with a previously established, well-tolerated regimen of oral irinotecan in adolescent and young adult cancer patients 13-30 years old. This age range was chosen because the likely clinical application for this drug pair will be in the treatment of pediatric-type sarcomas (e.g., Ewing sarcoma, osteosarcoma), which more often occur in adolescents and young adults. Further, the age and size of these patients will preclude the need for additional dose-finding studies for eribulin, as would be necessary if small children were included.

In adults, combination trials using eribulin with agents like carboplatin and cyclophosphamide are underway in non-small cell lung cancer, ovarian carcinoma, and breast cancer. These drug partners all are myelosuppressive. A more attractive partner may be one with non-overlapping dose-limiting toxicities like irinotecan. When given on a protracted 5-day schedule, irinotecan does not cause severe myelosuppression, making it attractive for combination with eribulin. Oral administration of irinotecan used alone and in combination therapy has been extensively tested in pediatrics in 5 clinical trials involving 158 patients, and provides a convenient and cost-effective method for the protracted administration schedules which have shown greatest activity against pediatric tumors. Importantly, the dose-limiting toxicity of protracted irinotecan is diarrhea, with only minimal myelosuppression. In addition, the combination of microtubule inhibitors and camptothecins is supra-additive, and is routinely used in COG studies which administer vincristine with 5-day cycles of irinotecan. Thus, this combination is attractive for study because of the potential for therapeutic synergy and the likelihood that both agents may be able to be administered at full dosage.

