5.6 Dose Escalating Criteria

A 3 + 3 design will be used to determine dose assignment for patients, as described in Section 13.2. Specifically, the following rules will apply for dose escalation:

- A. Evaluate 3 patients at $dose_k$:
 - 1. If 0 of 3 patients have DLT, then
 - i. If first cohort, increase dose to $dose_{k+1}$ and go to A.
 - ii. Otherwise, go to B.
 - 2. If 1 of 3 patients has DLT, then go to B.
 - 3. If more than 1 patient has DLT
 - i. If lowest dose, then go to C.
 - ii. Otherwise, decrease dose to $dose_{k-1}$ and go to A.
- B. Evaluate 3 additional patients at dose_k :
 - 1. If 0 or 1 of 6 patients has DLT, then increase dose to $dose_{k+1}$ and go to A.
 - 2. If 2 or more patients have DLT, then
 - i. If lowest dose, then go to C.
 - ii. Otherwise, decrease dose to $dose_{k-1}$ and go to A.
- C. Discontinue dose escalation/de-escalation.

Accrual will continue until the recommended phase II dose for a Phase II study (RP2D) is established and at least 6 patients have been treated at this dose. The RP2D is the highest dose level at which no more than 1 of 6 patients experiences first-cycle DLT. Doses higher than dose level 2 will not be studied in this trial. Once the RP2D is identified, an additional 10 patients will be enrolled at this dose level.

5.7 **Duration of Therapy**

In the absence of treatment delays due to adverse event(s), treatment may continue for up to 17 cycles until one of the following criteria applies:

• Disease progression

- Intercurrent illness that prevents further administration of treatment
- Unacceptable adverse event(s)
- Patient decides to withdraw from the study
- General or specific changes in the patient's condition render the patient unacceptable for further treatment in the judgment of the investigator.

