13. STATISTICAL CONSIDERATIONS

13.1 Study Design/Endpoints

A phase I, dose-escalation trial is proposed to determine the recommended phase II dose (RP2D) of escalating doses of eribulin in combination with standard-dose oral irinotecan. Cohorts of 3 patients per dose level are proposed using a 3+3 design [70, 71]. The following rules will be incorporated for dose escalation/de-escalation and establishing the recommended Phase II dose using the occurrence of DLT during the first cycle of therapy that is possibly, probably, or definitely attributable to study therapy.

A. Evaluate 3 patients at dose_k:

- 1. If 0 of 3 patients have DLT, then
 - i. If first cohort, increase dose to $dose_{k+1}$ and go to A.
 - ii. Otherwise, go to B.
- 2. If 1 of 3 patients has DLT, then go to B.
- 3. If more than 1 patient has DLT

- i. If lowest dose, then go to C.
- ii. Otherwise, decrease dose to $dose_{k-1}$ and go to A.
- B. Evaluate 3 additional patients at dose_k:
 - 1. If 0 or 1 of 6 patients has DLT, then increase dose to $dose_{k+1}$ and go to A.
 - 2. If 2 or more patients have DLT, then
 - i. If lowest dose, then go to C.
 - ii. Otherwise, decrease dose to $dose_{k-1}$ and go to A.
- C. Discontinue dose escalation/de-escalation.

The RP2D is defined as the highest dose level in which there is no more than 1 DLT in 6 patients. Ten additional patients will be enrolled at the RP2D level. Similar dose modifications as specified in Section 6 would be applied to these patients. Doses higher than dose level 2 will not be studied in this trial.

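### Prolonged Grade 3 diarrhea without appropriate supportive care is scored as no DLT, and the patient still counts toward 0-1 of 6

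*Combined protocol and SAP*

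**What the plan says.** Section 5.5.2 makes any attributable Grade 3 or 4 non-hematological toxicity a DLT, subject to listed exclusions. Two exclusions concern diarrhea. One covers Grade 3 diarrhea lasting 3 days or less. The other covers "Grade 3 diarrhea regardless of duration if patient did not receive appropriate supportive care", with cefixime, loperamide or atropine under Section 5.3 named as that care. Grade 4 diarrhea is not excluded.

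The count that decides the trial is small. Section 5.6 states: "The RP2D is the highest dose level at which no more than 1 of 6 patients experiences first-cycle DLT". Section 13.1 repeats the rule. After six patients at a level, Section 5.6 reads: "If 0 or 1 of 6 patients has DLT, then increase dose".

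Section 11.1.1 makes every patient evaluable for toxicity from first treatment. No section sets a narrower population for DLT assessment, makes evaluability depend on supportive care, or provides for replacing a patient.

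On the background risk, Section 2.4 says that "the dose-limiting toxicity of protracted irinotecan is diarrhea, with only minimal myelosuppression". Section 2.3 explains that prophylactic cephalosporins allowed the oral irinotecan MTD to rise by 50% to 90 mg/m²/dose for 5 days, which is the fixed dose used here.

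**The concern.** Without the supportive-care bullet, attributable Grade 3 diarrhea beyond 3 days would be a DLT. With it, the event disappears from the numerator while the patient remains in the denominator. The patient is then handled exactly like one who completed cycle 1 without dose-limiting toxicity. Yet a patient who had prolonged severe diarrhea without the intended care has not shown that the dose is tolerable. At most, the result under the intended regimen is unknown.

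The error has one direction: it can only lower the DLT count. The RP2D is the primary objective and rests on at most six patients per level, so one reclassified patient can change the decision. The plan has little to correct this later, because the 10 expansion patients are treated at the chosen level without a DLT limit of their own.

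The trigger is also hard to apply consistently. The plan gives no adherence threshold and names no one to judge whether care was appropriate. Section 5.3.5 continues the antibiotic until 3 days after the last irinotecan dose, whereas Section 8.2.5 says 2 days. Section 5.3.6 has loperamide provided to each family, whereas Appendix E tells the family to buy it. The Appendix F diary has no entry for atropine.

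**Working it through.** **Plan's own figure.** The documents give no target DLT rate and no operating characteristics for the 1-of-6 rule, so there is no stated probability to reproduce. The rule itself is the only anchor.

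**Count level (no assumptions).** Take six patients at a level, two with attributable Grade 3 diarrhea lasting more than 3 days and no other DLT.
- Both had appropriate care: 2 of 6, and the level fails.
- One lacked it: 1 of 6, and the level passes.

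**Probability level (assumed inputs).** Let p be the true DLT rate, s the share of true DLTs that are Grade 3 diarrhea beyond 3 days with no other DLT, and m the share of those cases without appropriate care. The documents give none of the three. Every such event is taken as a true DLT.

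- Rate as scored: p' = p(1 − s·m)
- Chance the level passes: P(0-1 of 6) = (1 − p')^6 + 6·p'·(1 − p')^5

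With no exclusion and p = 0.33: 0.67^6 + 6 × 0.33 × 0.67^5 = 0.0905 + 0.2673 = 0.358.

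| p | s | m | p' | P(0-1 of 6) |
|---|---|---|---|---|
| 0.33 | none excluded | | 0.33 | 35.8% |
| 0.33 | 0.20 | 0.10 | 0.33 × 0.98 = 0.3234 | 37.1% |
| 0.33 | 0.50 | 0.20 | 0.33 × 0.90 = 0.297 | 42.7% |
| 0.33 | 0.50 | 0.50 | 0.33 × 0.75 = 0.2475 | 54.0% |
| 0.40 | none excluded | | 0.40 | 23.3% |
| 0.40 | 0.20 | 0.10 | 0.40 × 0.98 = 0.392 | 24.6% |
| 0.40 | 0.50 | 0.20 | 0.40 × 0.90 = 0.36 | 30.1% |
| 0.40 | 0.50 | 0.50 | 0.40 × 0.75 = 0.30 | 42.0% |

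**Would dropping only the affected patients be enough?** If only patients with the excluded diarrhea leave the denominator, the scored rate is p' / (1 − p·s·m).
- p = 0.33, s = 0.50, m = 0.20: 0.297 / 0.967 = 0.307, giving 40.5%. Recovered: (42.7 − 40.5) / (42.7 − 35.8) = 32% of the shift.
- p = 0.33, s = 0.50, m = 0.50: 0.2475 / 0.9175 = 0.270, giving 48.8%. Recovered: (54.0 − 48.8) / (54.0 − 35.8) = 29%.
- p = 0.40, same two cases: 27.4% and 35.1%, recovering about 39% and 37%.

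This partial change removes only about 30 to 40% of the shift. Patients who lacked care and happened not to have diarrhea would remain as DLT-free, so the denominator would depend on the outcome.

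**The case against.** The exclusion is a reasoned choice. Only eribulin is escalated. Irinotecan is fixed at a dose that Section 2.3 says was reached with cephalosporin cover, and Section 2.2 reports no Grade 3 or higher diarrhea on eribulin in the cited Phase III trial. Diarrhea in a patient who missed that cover is weak evidence against the eribulin level, and scoring it as a DLT could reject a level wrongly. This stands. It argues against calling every such event a DLT, but it does not justify counting the patient as tolerating the dose.

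Other limits also stand. Grade 4 diarrhea remains a DLT, as do Grade 3 electrolyte disturbances that do not improve within 7 days. Section 13.4 lists adverse events with severity, duration and attribution, so the events will be visible, although that does not alter the count used for decisions. Cefixime is on the delivery map and in the diary, so missed care may be uncommon.

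A reader might infer two stronger things from the text, and the documents support neither.
- *That diarrhea is the expected dose-limiting toxicity of the combination.* The statement in Section 2.4 concerns protracted irinotecan alone. For eribulin, Section 2.2 names neutropenia, leukopenia and peripheral neuropathy. Diarrhea is one expected DLT among several.
- *That any single missed measure, such as no intravenous atropine, excuses the event.* The bullet refers to appropriate care under Section 5.3. Section 5.3.6 ties atropine to onset within 4 hours of irinotecan, and loperamide to later onset or atropine failure. Late diarrhea treated with loperamide alone is therefore appropriate care. The list joined by or is loose, but it does not compel the wider reading.

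**Conclusion.** The concern holds in a limited form. The plan counts a patient whose DLT status under the intended regimen is unknown as DLT-free, and the resulting bias favors accepting a dose. The count-level effect is certain: one such patient turns 2 of 6 into 1 of 6.

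The effect on probability is not established. At a true rate of 33% the chance of passing rises from 36% to between 37% and 54% over the assumptions shown, and at 40% from 23% to between 25% and 42%. A reader might take the upper ends as the expected size. The documents do not support that, because they give no DLT mix and no rate of missed care. The baselines of 36% and 23% also treat every excluded event as a true DLT. If the target is the DLT rate under appropriate care, some of these events would not have occurred and the shift is smaller.

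**What to change.** In Sections 5.5.2, 5.6 and 13.1, define DLT evaluability for cycle 1 by objective receipt of the supportive care in Section 5.3. Judge it the same way for every patient, whether or not diarrhea occurred, with loperamide and atropine assessed only where Section 5.3.6 calls for them. A patient who did not receive that care and has no DLT is not DLT-evaluable and is replaced in the 3 or 6. Any other DLT still counts. Reconcile Section 5.3.5 with 8.2.5 on the antibiotic stop, and Section 5.3.6 with Appendix E on loperamide supply, so that the criterion can be applied. Before the RP2D is declared, also report the DLT count at that level with the excluded Grade 3 diarrhea events counted as DLTs.

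**Cost.** Some rewording, one extra line in the RP2D summary, and an occasional extra patient at a level. How occasional depends on how often care is missed. If share m of all patients lack care regardless of outcome, the evaluable fraction is (1 − m) + m·p(1 − s).
- p = 0.33, s = 0.20, m = 0.10: 0.90 + 0.0264 = 0.926, so 6 / 0.926 ≈ 6.5 patients are enrolled for six evaluable.
- p = 0.33, s = 0.50, m = 0.20: 0.80 + 0.033 = 0.833, so 6 / 0.833 ≈ 7.2.

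Keeping other DLTs from patients who lacked care tilts the count toward caution: in the second case the scored rate is 0.297 / 0.833 = 0.357 against 0.33. Section 13.2 should say whether replacements count toward its accrual total.
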